### Cardiovascular

- QTc prolongation: > 60 msec increase
- Serious cardiac disorders adverse event

### Liver function

- Hy's Law case: Serum total bilirubin  $\geq 2$  and ALT  $\geq 3$  for at least one visit during the double-blind treatment period

### Metabolic function

- Serious hypoglycemia adverse event
- Treatment emergent HbA1c: Shift from low/normal at baseline to high at least once during the double-blind treatment period

**Renal function**

- Treatment emergent abnormal eGFR: Shifts
  - Mild at baseline to moderate/severe during the double-blind treatment period
  - Moderate at baseline to severe during the double-blind treatment period

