2.3.1. Risk Assessment

Potential Risk of Clinical Significance	Summary of Data/Rationale for Risk	Mitigation Strategy
Study Intervention LY3016859		
Development of treatment-emergent anti-drug antibodies (TE ADA).	Incidence of TE ADA was 50% after a single dose, and up to 57% after multiple doses.	Collect samples up to 20 weeks after last dose to characterize ADA profile.
IV infusion may be associated with infusion reactions and hypersensitivity reactions.	LY3016859 is a monoclonal antibody that will be administered via IV infusion. Hypersensitivity reactions and infusion reactions may occur during treatment with such agents.	Monitor infusion reactions and hypersensitivity reactions. Guidance on management of infusion and hypersensitivity reactions are in Sections 8.2.1. and 8.2.2.
Dermatological adverse reactions similar to EGFR antagonists	One healthy participant who received a single dose of 1 mg LY3016859 experienced a rash that was considered similar to those associated with EGFR antagonists.	Collect dermatological AEs. Stop dosing for severe dermatological AEs.
Changes in eGFR in participants with diabetic nephropathy (DN)	A modest and non-statistically significant decrease in eGFR was observed in participants with DN who received LY3016859 in Part B of Study TGAB, but not in healthy participants in Study TGAA.	Exclude participants with moderate or severe renal impairment in the study. Short dosing duration. Monitor eGFR and stop dosing if necessary. CCI [REDACTED]
Fetal harm due to in utero exposure	No effects on embryo-fetal development in enhanced pilot embryo-fetal development studies in rats and rabbits. Definitive developmental and reproductive toxicity studies are not yet completed.	Do not enroll women who are pregnant or breastfeeding in studies for LY3016859.
Study Procedures		
Participant may experience increased OA symptoms.	Medications that relieve OA pain will not be allowed until Visit 801.	Rescue medication is permitted. Standard treatment of OA may be restarted after Visit 801 based on investigator discretion.

Abbreviations: ADA = anti-drug antibodies; AE = adverse events; DN = diabetic nephropathy; EGFR = epidermal growth factor receptor; eGFR = estimated glomerular filtration rate; IV = intravenous; OA = osteoarthritis; TE = treatment emergent; TGAA = study I5V-MC-TGAA; TGAB = study I5V-MC-TGAB.

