5.2. Exclusion Criteria

Participants are excluded from the study if any of the following criteria apply:

Medical Conditions

- [1003] have had an intra-articular injection of hyaluronic acid within 24 weeks of Visit 2
- [1004] have an eGFR of less than 70 ml/min/1.73m² based on CKD-EPI formula at Visit 1 or Visit 2
- [1005] Have any clinically serious or unstable cardiovascular, musculoskeletal disorder, gastrointestinal, endocrinologic, hematologic, hepatic, metabolic, urologic, pulmonary, dermatologic, immunologic, or ophthalmologic disease within 3 months of Visit 3

Prior/Concomitant Therapy

- [1006] have received any antibodies against nerve growth factor (NGF), or antibodies against EGFR, or EGFR tyrosine kinase inhibitors
- [1007] have a history of allergic reactions to monoclonal antibodies, or clinically significant multiple or severe drug allergies, including but not limited to erythema multiforme major, linear immunoglobulin A dermatosis, toxic epidermal necrolysis, or exfoliative dermatitis
- [1008] have a history or presence of uncontrolled asthma, eczema, significant atopy, significant hereditary angioedema or common variable immune deficiency, and

Reproductive

- [1009] are women who are pregnant or breastfeeding.

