8.2.3. Adverse Events of Special Interest

Dermatological adverse reactions

EGFR antibodies or EGFR-associated tyrosine kinase inhibitors are associated with various dermatological AEs, including acneiform rashes, xerosis, pruritis, and photosensitivity. Secondary infection can also develop.

Participants should use sun protection during the study period. Dermatological adverse reactions should be managed by the investigator according to standard of care. Discontinuation of treatment may be considered if these AEs do not respond to topical treatment or are widespread (>30% body surface area) or are severe.

If any of these AEs are reported, sites will be prompted to provide additional information.

Renal Function

Changes in eGFR were observed in participants with diabetic nephropathy in Study TGAB (Section 2.2). Such changes were reversible and were not associated with increase in proteinuria. Blood and urine samples will be collected to characterize the effects of LY3016859 on renal function and eGFR will be monitored during the study.

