## 6.17. Totality of Evidence for Safety

The totality of evidence for safety analysis has been briefly described in the H0P-MC-CPMP SAP Version 5. The key safety events to be considered for H0P-MC-OA01 are listed below by domain:

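### The SAP 6.17 eGFR safety item has no row starting from normal eGFR, so a fall from normal to moderate or severe is not counted while a smaller fall from mild is

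*SAP*

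**What the plan says.** SAP 6.17 introduces its list with "The key safety events to be considered for H0P-MC-OA01 are listed below by domain". Under Renal function, treatment-emergent abnormal eGFR is made up of two shifts:

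- "Mild at baseline to moderate/severe during the double-blind treatment period"
- "Moderate at baseline to severe during the double-blind treatment period"

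Under Metabolic function in the same list, the HbA1c item reads "Shift from low/normal at baseline to high at least once during the double-blind treatment period".

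On who can enter, exclusion criterion [1004] in Protocol 5.2 removes people who "have an eGFR of less than 70" mL/min/1.73 m² at Visit 1 or Visit 2. It sets no upper limit. The mitigation column in Protocol 2.3.1 says "Exclude participants with moderate or severe renal impairment in the study".

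On the earlier renal signal, Protocol 2.3.1 reports that "A modest and non-statistically significant decrease in eGFR was observed in participants with DN" and that it was not seen in healthy participants. Protocol 8.2.3, which lists renal function among the adverse events of special interest, adds: "Such changes were reversible and were not associated with increase in proteinuria".

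**The concern.** Given the entry criteria, participants should start with normal or mildly reduced eGFR. The 6.17 item covers the second group but not the first, and spends its other row on a group the protocol sets out to exclude. To reach a given on-treatment value, someone who starts normal must lose more function than someone who starts mild. The rule therefore counts the smaller loss and leaves out the larger one.

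The HbA1c item names its unaffected starting state, and nothing in the visible text explains why the eGFR item does not. At stake is the sensitivity of one item in the key safety list, on a topic the protocol treats as of special interest.

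**Working it through.** The plan gives no figure to reproduce here, so the check is one of logic followed by a sensitivity range.

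**Step 1. Apply the rule.** The visible text gives no eGFR cut-offs. I assume normal at 90 or above, mild 60 to 89, moderate 30 to 59 and severe below 30.

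| Baseline | On treatment | Shift | Fall | Counted in 6.17? |
|---|---|---|---|---|
| 70 | 59 | mild to moderate | 11 (16%) | yes |
| 89 | 59 | mild to moderate | 30 (34%) | yes |
| 90 | 59 | normal to moderate | 31 (34%) | no |
| 100 | 45 | normal to moderate | 55 (55%) | no |
| 110 | 29 | normal to severe | 81 (74%) | no |

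No baseline of 70 or above is moderate. The second row can be populated only if eGFR drops between the eligibility visits and baseline. The ordering does not depend on the exact cut-offs.

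**Step 2. How many start normal.** The documents give no baseline distribution. I assume a normal distribution with mean m of 80, 85, 90 or 95 and SD s of 12, 14 or 16, truncated at 70:

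P(eGFR ≥ 90 | eGFR ≥ 70) = [1 − Φ((90 − m)/s)] / [1 − Φ((70 − m)/s)]

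- Minimum (m = 80, s = 12): 0.2023 / 0.7977 = 0.254
- Maximum (m = 95, s = 12): 0.6615 / 0.9814 = 0.674

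The Protocol Synopsis gives 84 on LY3016859 and 41 on placebo. The numbers starting normal are then 84 × 0.254 = 21 to 84 × 0.674 = 57, and 41 × 0.254 = 10 to 41 × 0.674 = 28.

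**Step 3. How many events would be missed.** I assume one post-baseline value per participant and a log change distributed N(μ, σ²). With f the truncated baseline density:

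Missed = 84 × ∫ from 90 upward of f(b) · Φ((ln(60/b) − μ)/σ) db

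Counted = the same integral from 70 to 90.

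Median fall = 1 − exp(μ). Mean fall = 1 − exp(μ + σ²/2). The chance of missing at least one event is 1 − exp(−missed).

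| μ, σ | Median (mean) fall | Missed per 84 | Counted per 84 | Chance of missing at least one |
|---|---|---|---|---|
| −0.05, 0.12 | 4.9% (4.2%) | 0.0095 to 0.0135 | 0.65 to 2.82 | about 1% |
| −0.10, 0.15 | 9.5% (8.5%) | 0.19 to 0.29 | 2.4 to 8.3 | 17% to 25% |
| −0.10, 0.20 | 9.5% (7.7%) | 0.74 to 1.32 | 4.0 to 12.0 | 52% to 73% |
| −0.20, 0.20 | 18.1% (16.5%) | 1.95 to 3.67 | 7.6 to 21.5 | 86% to 97% |

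In the last row, missed events are 8% to 32% of all falls below 60. In the first row they are 0.3% to 2.0%. The reason is that reaching 60 from a baseline of 90 takes a loss of 1 − 60/90 = 33%.

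**The case against.** The strongest objection is that the categories are not visible. SAP 6.12.4, whose renal analysis was updated in Version 4, is redacted. The master SAP, which also describes the totality-of-evidence analysis, was not available. Either could define mild to include normal or add the missing row, and redacted text is not missing from the plan. This stands as a limit on the conclusion. It does not remove the point, because the two shifts in 6.17 are themselves fully visible and no visible text says that mild includes normal.

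A second objection is that the effect is close to nil for the signal the protocol describes, and that large falls would appear elsewhere: in the final-lock eGFR shift table (SAP 8), and, if reported, among the renal events of special interest (SAP 6.12.3) or discontinuations due to adverse events. No visible decision rule uses the 6.17 count. All of this is right and keeps the point minor, but none of those outputs corrects the 6.17 count itself.

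Three smaller points also stand:

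- The single-value model is illustrative. The rule covers the whole double-blind period, and repeated values could raise both missed and counted events.
- HbA1c is judged against a laboratory range and not by grades of impairment, so the comparison is suggestive only.
- A nearly empty moderate row does no harm in itself.

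**Conclusion.** The concern holds as written, at minor severity. The visible definition leaves out a starting group that the entry criteria admit, and it ranks falls in the wrong order. This lowers the sensitivity of one key safety item in both arms and does not bias the comparison between them.

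The loss is negligible for a modest eGFR decrease. It becomes material only with large falls, which no visible passage predicts. These sizes rest on the assumed cut-offs, baseline distribution and change model. Confidence is medium because the category definitions may sit in text that cannot be seen.

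**What to change.** Reword the first row of the eGFR item so that it counts a shift from normal or mild at baseline to moderate or severe during the double-blind treatment period. If mild is already meant to include normal, say so in 6.17 and give the cut-offs.

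The Revision History shows that 6.17 was added before unblinding for the PoC lock. A change made after that lock should be labelled as such, with counts reported under both definitions.

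The cost is one reworded row and, after the PoC lock, one extra count per arm. No new data are needed, since eGFR is already monitored and tabulated in the final-lock shift table.

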**Dermatological**

- Serious or severe dermal reactions

**Hypersensitivity**

- Moderate to severe infusion site reactions
- Serious or severe hypersensitivity reactions

**6.18. Annual Report Analyses**

Analyses will be produced as needed for the purposes of providing periodic safety reviews to regulatory agencies (e.g. Development Safety Update Reports.) Data from this ISA will be combined with data from other clinical studies that investigated LY3016859. In all analyses, a combined LY arm will be created which includes participants assigned to any dose of LY3016859 in the included studies, including LY-combination regimens.

The following data will be summarized by treatment group.

- Enrollment (ongoing and completed)
- Demographics (Race, ethnicity, and gender)
- Exposure
  - Cumulative number of subjects exposed to LY3016859
  - Cumulative number of subjects exposed to LY3016859 by age
  - Cumulative number of subjects exposed to LY3016859 by sex
  - Cumulative number of subjects exposed to LY3016859 by race
- Cumulative summary of serious adverse events

The following listings will be provided.

- List of serious adverse events during the reporting period
- List of subjects who died
- Cumulative list of subjects who discontinued due to an adverse event (discontinued from treatment or study)
- List of subjects who discontinued due to an adverse event during the reporting period

Additional analyses may be added or omitted at the time of report submission as needed.

**6.19. Clinical Trial Registry Analyses**

Additional analyses will be performed for the purpose of fulfilling the Clinical Trial Registry (CTR) requirements.

Analyses provided for the CTR requirements include the following:

Summary of adverse events, provided as a dataset, which will be converted to an XML file. Both Serious Adverse Events and 'Other' Adverse Events are summarized: by treatment group, by MedDRA preferred term.

- A serious adverse event is an adverse event that is considered 'Serious' whether it is a treatment emergent adverse event (TEAE).
- An adverse event is considered in the 'Other' category if it is both a TEAE and is not serious. For each Serious AE and 'Other' AE, for each term and treatment group, the following are provided:
  - the number of participants at risk of an event
  - the number of participants who experienced each event term
  - the number of events experienced.
- Consistent with [www.ClinicalTrials.gov](http://www.ClinicalTrials.gov) requirements, 'Other' AEs that occur in fewer than 5% of participants in every treatment group may not be included if a 5% threshold is chosen (5% is the minimum threshold).
- AE reporting is consistent with other document disclosures for example, the CSR, manuscripts, and so forth.

A summary of a baseline characteristics XML file will be provided.

## 7. Unblinding Plan

The general unblinding plan is described in the H0P-MC-CPMP SAP Version 5. Unblinding considerations specific to H0P-MC-OA01 are provided below.

### **Immunogenicity Analysis Planning**

To support the assessment committee's evaluation of immunogenicity, a limited number of preidentified individuals may also gain access to the unblinded data. The project statistician will work with the clinical immunogenicity scientist and clinical lab data scientist to determine an appropriate amount of ISA-level data to support this objective. The timing of the transfer of treatment assignment and immunogenicity data will be based on this collaboration. Information that may unblind the study during the analyses will not be reported to study sites or the blinded study team until the study has been unblinded.

## 8. Reports to be Generated at Final Database Lock

The following analysis will be performed for final database lock.

- Patient disposition - the analysis of patient disposition conducted in POC lock will be conducted for double-blind treatment and safety follow-up period combined.
- eCOA compliance - the overall eCOA compliance analysis conducted in POC lock will be summarized for the PDEP period plus at each nominal week up to Visit 801.
- Concomitant therapy – the analysis conducted in POC lock will be repeated including safety follow up period combined (may also include PDEP) except the listing of rescue medication use above protocol specified limits.
- Efficacy endpoint – The weekly average pain intensity via NRS will be calculated with extension to week 12 (Visit 801). The following analysis will be conducted across all time points in the double-blinded treatment and safety follow-up period combined (DB plus FU) based on the same model conducted in DB treatment period only.
  - Change from baseline in average pain intensity measured by weekly average of NRS
  - Change from baseline in worst pain intensity measured by weekly average of NRS
  - Change from baseline in DSA-specific physical functioning measures
  - Proportion of participants with a pain reduction from baseline greater than or equal to 30%, 50%, and 70% as measured by the average pain responses on the NRS
  - Proportion of participants with reduction from baseline greater than 30%, 50%, and 70% on DSA-specific physical function subscale
  - Overall improvement as Measured by Patients' Global Impression of Change (PGI)

A frequentist MMRM analysis will be conducted as a sensitivity analysis for the primary and some secondary endpoints.

A Bayesian MMRM subgroup analysis of baseline pain severity ( $<7$ ,  $\geq 7$ ) will be also evaluated for the primary and key secondary endpoint. A frequentist MMRM analysis will be performed as a sensitivity analysis for subgroup analysis.

- Safety analyses for TEAEs – the following analysis will be repeated including double-blind and safety follow-up period unless otherwise specified.
  - Overview of adverse event
  - SAE and a listing of SAE

- TEAE and Post-treatment emergent adverse event (PTEAE) by PT, by PT within SOC. A listing of TEAE and PTEAE will be provided.
- Post-treatment emergent AE by PT, by PT within SOC for safety follow-up period only
- Adverse event of special interest (ISA specific)
- Laboratory measures – the analysis conducted in POC lock will be repeated in DB plus FU period. The additional analysis will be included
  - The shift table of eGFR at baseline vs. postbaseline by minimum, maximum and last observed eGFR result will be summarized.
  - Summary of treatment-emergent ADA positive anytime in DB treatment period by ADA positive titer status at the last non-missing assessment in safety follow-up period will be presented by treatment.
  - A shift table of ADA from maximum baseline ADA titer to maximum postbaseline ADA titer in LY3016859 arm will be reported.
  - A listing of participants with ADA Detected at any time for safety population will be provided.
  - Summary of hepatic function laboratory maximum observed result will be presented.
- Vital signs – the analysis conducted in POC lock will be repeated for combined DB plus FU period.
- ECG - the analysis conducted in POC lock will be repeated for combined DB plus FU period. Additionally, a summary of ECG measures and boxplot will be provided as well as a listing of out of range of ECGs.
- Protocol deviations - the analysis conducted in POC lock will be repeated for combined DB plus FU period.

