1.3. Schedule of Activities (SoA)

This SoA shows visits and procedures unique to the intervention-specific appendix (ISA) H0P-MC-OA01 (OA01) for LY3016859. Please refer to master protocol H0P-MC-CPMP (CPMP) and the osteoarthritis (OA) disease-state addendum (DSA) H0P-MC-CPMP(1) SoAs for additional information.

H0P-MC-OA01 ISA	Randomization	Double-Blind Treatment				Follow-up			Early Discontinuation	Notes
Visit Number	V3	V4	V5	V6	V7	V801	V802	V803	ED	
Study Week	0	2	4	6	8	12	16	26		
Visit Window (days)		±3	±3	±3	±3	±5	±7	±7		Minimal interval between 2 doses cannot be shorter than 11 days.
Physical examination	X	X	X	X	X	X	X	X	X	Targeted exam for skin, eyes, mouth, lungs and GI tract should be performed at each visit, in addition to any symptom driven exam. Full physical exam should be performed at Visit 803 or ED.
Weight								X		
Vital signs	X	X	X	X	X	X	X	X		Includes respiratory rate, blood pressure, temperature and pulse rate. All vital signs are collected before study intervention infusion on V3-6.
ECG			X		X			X		Single safety ECGs
Study intervention IV infusion	X	X	X	X						1 hour IV administration The timing between randomization and the first IV infusion may be up to, but not longer than 2 business days to reduce participant burden.
Adverse events						X	X	X		
Concomitant medication						X	X	X		
Rescue medication usage reporting						X				If the participant discontinues after V801, this assessment is not needed for ED per the CPMP SoA.
NRS						X				If the participant discontinues after V801, this assessment is not needed for ED per the CPMP SoA.
PGI						X				If the participant discontinues after V801, this assessment is not needed for ED per the CPMP SoA.

H0P-MC-OA01 ISA	Randomization	Double-Blind Treatment				Follow-up			Early Discontinuation	Notes
Visit Number	V3	V4	V5	V6	V7	V801	V802	V803	ED	
Study Week	0	2	4	6	8	12	16	26		
Visit Window (days)		±3	±3	±3	±3	±5	±7	±7		Minimal interval between 2 doses cannot be shorter than 11 days.
WOMAC						X				If the participant discontinues after V801, this assessment is not needed for ED per the CPMP SoA.
C-SSRS						X		X		Use C-SSRS Since Last Visit version.
Self-Harm Supplement Form						X		X		
Self-Harm Follow-up Form						X		X		Required if triggered by the Self-Harm Supplement Form per instructions.
Hematology						X	X	X		
Chemistry		X		X		X	X	X		
Urine Chemistries	X	X	X	X	X	X		X	X	
Urinalysis								X		

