- the site completes all procedures and sample collection noted in the SoAs
- no intervention is administered at this visit, and
- the site instructs participants to continue with study restrictions and NRS diary entries before their visit discharge.

Post-treatment Follow-up Period (Visits 801-803)

Participants must complete 3 post-treatment follow-up visits for safety, PK and immunogenicity assessment at Visits 801-803, according to the SoA.

The site schedules Visit 801 approximately 4 weeks after Visit 7.

At Visit 801, participants return the device for NRS diary collection.

At Visit 803, the participants are discharged from the study.

If the participant receives at least one dose of intervention and discontinues during the double-blind treatment period, they should complete early discontinuation procedures per the CPMP Protocol SoA and Visit 801 should be scheduled approximately 30 days after the last dose of study intervention.

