4.1. Scientific Rationale for Study Design

The master protocol describes the overall study design rationale.

Efficacy data will be collected up to 6 weeks after the last dose, based on the long PK half-life and potential sustained target engagement of LY3016859.

Safety, PK, PD and immunogenicity samples will be collected up to 20 weeks after the last administration of intervention to characterize the safety and clinical immunogenicity profile.

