### 4.2. Secondary Objectives

Secondary objectives applicable to all ISAs are listed in the H0P-MC-CPMP SAP Version 5.

The key secondary objective for H0P-MC-OA01 is to evaluate whether LY3016859 is superior to placebo in reducing pain as measured by the mean change from baseline assessment to Week 8 for pain intensity measured by the Western Ontario and McMaster University Arthritis Index (WOMAC®) Pain Subscale.

Additional secondary endpoints specific to H0P-MC-OA01 are listed below.

Objective	Endpoint Measure
Other Secondary	
Physical Functioning Efficacy of LY3016859 versus placebo	
 
• Change from baseline to endpoint for WOMAC® for               
 
○ stiffness subscale
 
○ physical function subscale
 
 
 
• Proportion of participants with reduction from baseline greater than 30%, 50%, and 70% on WOMAC pain subscale across all time points
 
• Proportion of participants with reduction from baseline greater than 30%, 50%, and 70% on WOMAC physical function subscale across all time points
 
• Proportion of participants with reduction from baseline greater than 30%, 50%, and 70% on WOMAC stiffness subscale across all time points
 
• Time to first treatment response with at least 30%, 50%, and 70% reduction from baseline in WOMAC pain subscale
 

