**Key Secondary Analysis**

A Bayesian longitudinal mixed-model repeated measures analysis (MMRM) will be performed to evaluate the change from baseline to each post baseline visit for the WOMAC® pain subscale, physical function subscale, and stiffness subscale. The model will utilize the constrained cell means model so that a common mean is estimated at the baseline. More details on this approach are provided in the H0P-MC-CPMP SAP Version 5.

This table describes information included in the model.

Categorical factors	
 
• the interaction of treatment and timepoint (constrained to estimate a common mean at baseline across treatments)
 
• average baseline pain severity category (baseline NRS < 7, baseline NRS >= 7)
 
• pooled investigative site
 

Continuous covariates	
 
• none
 

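### Does SAP Section 8 need its own rule for early discontinuers' Visit 801 scores before extending PGI and WOMAC function analyses to Week 12?

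*SAP*

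**What the plan says.** SAP Section 8 lists the efficacy outputs for final lock: "The following analysis will be conducted across all time points in the double-blinded treatment and safety follow-up period combined (DB plus FU". They are to be "based on the same model conducted in DB treatment period only". The list names PGI and "Change from baseline in DSA-specific physical functioning measures". WOMAC is not named there. It enters through SAP 4.2, where the Physical Functioning row holds change in WOMAC stiffness and function and responder endpoints such as "Proportion of participants with reduction from baseline greater than 30%, 50%, and 70% on WOMAC physical function subscale across all time points". Change in WOMAC pain, the key secondary measure, is not clearly in the Section 8 list.

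Visit 801 has two timings. For completers it is about 4 weeks after Visit 7, and the Schedule of Activities labels it Week 12 with a window of 5 days either side. For participants who received at least one dose and discontinued during double-blind treatment, Protocol Section 4 and SAP 5.1 both say that "Visit 801 should be scheduled approximately 30 days after the last dose of study intervention".

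After Week 8, Visit 801 is the only scheduled visit with WOMAC and PGI. On the early discontinuation visit, the schedule notes: "If the participant discontinues after V801, this assessment is not needed for ED per the CPMP SoA". This implies that both are collected at that visit when a participant stops before Visit 801.

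The WOMAC model in SAP 6.10.3 is there "to evaluate the change from baseline to each post baseline visit", with time as a categorical factor. SAP 6.1 and 6.3 leave other general considerations and missing data to the CPMP SAP Version 5.

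**The concern.** One visit number covers two different times. If records are placed by visit number, a score taken as early as Week 4.3 would be analysed as Week 12. The two groups also differ in exposure. A completer at Week 12 is six weeks past a fourth dose, while an early discontinuer is about 30 days past a first, second, third or fourth dose.

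This bears on the purpose of the follow-up. Protocol 4.1 says "Efficacy data will be collected up to 6 weeks after the last dose" and gives the long half-life and possible sustained target engagement as the reason. A Week 12 mean that mixes the two groups would answer that question less cleanly. Endpoints could also disagree about who is observed at Week 12: NRS is averaged by nominal week, so an early discontinuer would have no Week 12 NRS value but could have a Week 12 WOMAC or PGI score.

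**Working it through.** **Inputs.** Infusions at Weeks 0, 2, 4 and 6, i.e. days 0, 14, 28 and 42 (Protocol 1.2 and 1.3). Visit 801 at Week 12 ± 5 days (Protocol 1.3). About 30 days after the last dose for early discontinuers (Protocol 4, SAP 5.1). 125 randomised, 15% dropout, about 107 completers (Protocol 1.1 and 9.2, SAP 5.2).

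**The plan's own figure.** 125 × (1 − 0.15) = 106.25, against a stated 107. This agrees to within rounding.

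**Week 12 window.** 84 − 5 = day 79 to 84 + 5 = day 89. For completers, time since last dose is 84 − 42 = 42 days.

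**Early discontinuers.** Visit 801 day = day of last dose + 30; shortfall = 79 − that day.

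| Last dose | Visit 801 | Study week | Days before window opens | Weeks before Week 12 |
|---|---|---|---|---|
| day 0 | day 30 | 4.29 | 49 | 7.71 |
| day 14 | day 44 | 6.29 | 35 | 5.71 |
| day 28 | day 58 | 8.29 | 21 | 3.71 |
| day 42 | day 72 | 10.29 | 7 | 1.71 |

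All four nominal days fall before the window. A Week 6 dose given 3 days late puts the visit on day 45 + 30 = 75, still 4 days short. Reaching day 79 then takes a visit 79 − 45 = 34 or more days after the dose, which an approximate 30-day rule could allow. A late Week 4 dose with a visit 5 days late gives 31 + 35 = day 66, still outside.

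**How many.** 125 − 107 = 18, or 125 × 0.15 = 18.75, so 18 to 19. With equal dropout that is 84 × 0.15 = 12.6 on LY3016859 and 41 × 0.15 = 6.15 on placebo.

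**Share of Week 12 scores.** If everyone attends: 18/125 = 14.4% to 19/125 = 15.2%. If half of the discontinuers attend (an assumption): 9/(107 + 9) = 7.8% to 9.5/(106 + 9.5) = 8.2%.

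**What a share of that size can do.** For a simple arm mean, shift = share × the gap between the early and the true Week 12 scores. Each 1-point gap moves the mean by about 0.15 point at full attendance and 0.08 at half. With equal shares in the arms, the treatment difference moves by share × (gap on LY3016859 − gap on placebo), which is zero if the gaps are equal. This is a scale conversion for raw means, not the model, and no bias is estimated.

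**What is at Week 12.** SAP 4.1 and 4.2 set the primary and key secondary endpoints at Week 8. No decision rule visible in either document uses Week 12 PGI or WOMAC, and SAP 6.4 plans no multiplicity adjustment.

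**The case for a change.** The best case for a change is that both ingredients are OA01's own. The 30-day timing stands in the OA01 protocol and SAP, and the follow-up analyses were added in Version 4 of the OA01 SAP. This SAP is therefore a natural home for the rule, and one sentence would supply it. SAP 6.10.3 also has the WOMAC responder model take in all post-baseline observations, which on a literal reading admits these scores. Date-based placement would need thought too, since days 44 and 58 lie close to Weeks 6 and 8.

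The timing mismatch and the silence of the two documents stand. The step from silence to mis-pooling does not. The OA01 SAP is a supplement to the CPMP SAP Version 5, and Section 8 reuses the double-blind model, so whatever that model does with records after discontinuation may carry over. Scores from the early discontinuation visit need the same kind of placement, which makes the CPMP level a likely place for the rule. For the key secondary endpoint, SAP 6.1 already takes a hypothetical approach to discontinuation.

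Nor is there one right answer to impose. Leaving the scores out of Week 12, placing them by actual day or summarising them by days since last dose are all reasonable. Leaving them out makes Week 12 lean more on the missing-data assumption. The hypothetical strategy in SAP 6.1 is defined for Week 8 and does not settle the matter, because completers are also off treatment at Week 12.

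Two wording points in SAP 6.1 are sometimes read together with this one. The treatment condition is defined whatever the adherence, and the population line names chronic pain rather than knee osteoarthritis. The first can mean missed or delayed infusions, and the section's clinical question and closing sentence both state the hypothetical strategy. The second is a slip, since the clinical question names knee osteoarthritis. Neither changes an analysis.

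**Conclusion.** No change to the plan is needed. This is missing detail that the analysis team can fill sensibly. Infusion dates are recorded (Protocol 6.4), and SAP 6.12.2 already works from the day of treatment discontinuation, so these Visit 801 records can be identified and kept apart from true Week 12 scores without new data.

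The reach is limited to PGI and the physical functioning outputs at final lock. NRS is averaged by nominal week and is not affected. The Week 8 endpoint definitions are unaffected. A Week 8 estimate would move only if post-discontinuation scores entered its model, which nothing in the documents shows.

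The size rests on three assumptions: the planned 15% dropout, attendance at Visit 801, and mapping by visit number. The 18 to 19 participants are a planning figure. Fewer will count if some were never dosed or do not return. A few more could count because Protocol 7.1 lets some participants stop treatment and remain in the study. The conclusion also allows for the CPMP SAP Version 5 either containing the rule or being silent. If it is silent, a sensible convention applied at programming and described in the study report is enough for supportive analyses of this kind.
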